2.2 Secondary Aims & Hypotheses

Secondary Aim 1: To identify the thresholds of harm for the associations of intraoperative chemical and mechanical power with postoperative pulmonary complications within seven days after surgery.

Secondary Hypothesis 1: The exposures to intraoperative chemical and mechanical power have thresholds of harm (inflection points) from which on the risk for postoperative pulmonary complications within seven days after surgery increases substantially.

Secondary Aim 2: To evaluate the interaction between the intraoperatively applied chemical and mechanical power on postoperative pulmonary complications within seven days after surgery.

Secondary Hypothesis 2: Chemical power-related harm largely depends on the concomitantly applied mechanical power, meaning that chemical power causes significantly more postoperative pulmonary complications within seven days after surgery when exposed to high intraoperative mechanical power.

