3.6.2 Inferential statistics

Primary aim:

We will summarize intraoperative chemical and mechanical power by calculating time-weighted averages for each patient. The influence of the intraoperatively applied time-weighted average chemical and mechanical power on composite postoperative pulmonary complications will be evaluated by multivariable logistic regression – estimating the odds ratios related to the effect of 1 unit increase in chemical or mechanical power. The regression model will be calculated with and without the above-mentioned confounders. We will consider the exclusion of a potential confounder if its inclusion results in a change in the regression coefficients (beta) for both exposures of less than 10%.

Secondary aim 1:

The relationship between varying levels of chemical / mechanical power and postoperative pulmonary complications will be analysed via multivariable logistic regression including cubic splines with up to five knots of chemical and mechanical power. We will further evaluate whether chemical and mechanical power have an upper threshold of harm, whereafter the odds for PPCs increase substantially by means of threshold regression. We will consider a 5% change in slope as clinically relevant, although there is no established minimal clinically important difference for PPCs, and this definition remains arbitrary.

Secondary aim 2:

We will evaluate the interaction between chemical power and mechanical power by implementing an interaction term for the intraoperatively applied time-weighted average mechanical power in the multivariable regression model performed to evaluate the primary aim. Additionally, we will analyse the effect of chemical and mechanical power on PPCs for 5 subsets of the study population stratified by chemical or mechanical power for each of the following patterns: 1) increasing chemical power and matched mechanical power, 2) matched chemical power and increasing mechanical power, 3) increasing chemical power and decreasing mechanical power, and 4) increasing chemical power and increasing mechanical power. Data will also be graphically presented with a 3D surface plot showing chemical and mechanical power on the x- and z-axes and the percentage of PPCs on the y-axis. Therefore, the population will be divided into equally sized groups including an certain fraction of patients of the ranges of both exposures.

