3.6.3 Tables and figures (planned)

Table 1: Patient characteristics

Demographics, respiratory risk factors, coexisting conditions, and surgery characteristics will be descriptively presented, grouped by low, moderate, marked, and substantial chemical power (<25%, 25-50%, 50-75%, and 75-100% quantile of mechanical power).

Table 2: Intraoperative mechanical ventilation parameters (alternatively as figure)

Intraoperative mechanical ventilation parameters will be descriptively presented, grouped by low, moderate, marked, and substantial chemical power (<25%, 25-50%, 50-75%, and 75-100% quantile of mechanical power)

Figure 1: CONSORT diagram

Figure 2: Ranges of chemical, mechanical, and mechanochemical power quartiles

Barplots showing the ranges of time-weighted averages of chemical, mechanical, and mechanochemical power for patients with low (first quartile: <25%), moderate (second quartile: 25-50%), marked (third quartile: 50-75%), and substantial (fourth quartile: 75-100%) power.

Figure 3 a/b (take-away-figure): Chemical and mechanical versus the risk of PPCs.

Smoothed spline regression curves with the odds ratios for each spline presenting the risk for PPCs over the observed ranges of chemical (a), and mechanical power (b).

Figure 4 a/b/c: Stratified analysis of chemical and mechanical power on PPCs

Bar plots on top: a) increasing chemical power and matched mechanical power, b) matched chemical power and increasing mechanical power, c) increasing chemical power and decreasing mechanical power, and d) increasing chemical power and increasing mechanical power. Error bars on bottom: corresponding relative risks of PPC, calculated for each subsample; error bars represent the 95% confidence interval.

Figure 5 (alternative take-away-figure): Chemical and mechanical versus the risk of PPCs

A 3D surface plot with chemical and mechanical power on the x- and z-axes and the percentage of PPCs on the y-axis. The population will be divided into equally sized groups including an applicable fraction of patients of the ranges of both exposures.

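### The interaction in Secondary aim 2 is tested only with linear main effects; with marked curvature and correlated exposures, curvature can pass for interaction or hide it

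*Combined protocol and SAP*

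**What the plan says.** Section 3.6.2 defines the primary-aim model as a logistic regression "estimating the odds ratios related to the effect of 1 unit increase in chemical or mechanical power". That is one slope per exposure, linear on the log-odds scale. Secondary aim 2 adds the interaction to this model, by "implementing an interaction term for the intraoperatively applied time-weighted average mechanical power in the multivariable regression model performed to evaluate the primary aim".

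Non-linear terms appear only under Secondary aim 1, which plans "multivariable logistic regression including cubic splines with up to five knots of chemical and mechanical power" together with threshold regression. For the threshold it adds: "We will consider a 5% change in slope as clinically relevant". Nothing carries the splines or the threshold into the interaction model, and no sensitivity analysis does so.

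Section 2.2 states the two hypotheses that meet here. Secondary Hypothesis 1 is that both exposures "have thresholds of harm (inflection points) from which on the risk for postoperative pulmonary complications within seven days after surgery increases substantially". Secondary Hypothesis 2 is that "Chemical power-related harm largely depends on the concomitantly applied mechanical power".

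Two other planned analyses bear on the point. Figure 3 (section 3.6.3) shows "Smoothed spline regression curves with the odds ratios for each spline", one panel per exposure. Secondary aim 2 also has four stratified patterns, shown in Figure 4 with "corresponding relative risks of PPC, calculated for each subsample; error bars represent the 95% confidence interval", and a 3D surface plot.

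**The concern.** The test of Secondary Hypothesis 2 assumes straight-line effects, while Secondary Hypothesis 1 expects bends in both. If the first hypothesis is true in a marked form, the model that tests the second is misspecified on the authors' own terms.

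When two exposures are correlated, their product partly tracks the square of each. A product term added to linear main effects then picks up curvature that the main effects cannot express. If risk bends upward and the correlation is positive, the error runs towards the synergy that the authors hope to find. If the correlation is negative, it runs the other way and can hide a real synergy.

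The product term is the only planned formal test of Secondary Hypothesis 2. The consequence would be a claim of synergy, or of none, that partly reflects the shape of the separate dose-responses.

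**Working it through.** The plan states no sample size, event rate, alpha or correlation, so there is no figure of its own to reproduce. The check is a short derivation followed by simulation under stated assumptions.

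**Step 1: direction and size of the bias.** Take standardised bivariate normal exposures X and Z with correlation ρ, and no interaction.

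- Cov(X², XZ) = 3ρ − ρ = 2ρ, and Var(XZ) = 1 + ρ².
- If each exposure has a quadratic component c, the product term takes up about 2 × c × 2ρ/(1 + ρ²) = 4ρc/(1 + ρ²). The sign is that of ρ times the curvature, and at ρ = 0 it vanishes. This ignores the logistic weights.
- For a hinge at +0.5 SD with slope change d, c = d × φ(0.5)/2, with φ(0.5) = 0.352.
- Flat, then odds ratio 2.0 per SD: d = ln 2 = 0.693, so c = 0.122. At ρ = 0.3 the spurious coefficient is 4 × 0.3 × 0.122/1.09 = 0.134, odds ratio 1.14. At ρ = 0.5 it is 0.195, odds ratio 1.22. Simulation of the planned model (30% complications) gave about 1.14 and 1.22.
- Plateau (odds ratio 1.6 per SD, then flat): c = −0.083. At ρ = 0.3 the coefficient is −0.091, odds ratio 0.91; simulation gave 0.92. So a plateau with positive correlation also hides synergy.

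**Step 2: inputs on the J/min scale.**

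- From the documents (section 3.4.1): chemical power = 141000 × [1.7×10⁻⁵ + (FiO₂ − 0.21) × 1.63×10⁻⁴], which is 2.4 J/min at FiO₂ 0.21 and 20.6 at 1.0. A value of 12 J/min corresponds to FiO₂ of about 0.63.
- Assumed exposures: FiO₂ mean 0.5, SD 0.15 (20% above 12 J/min); mechanical power lognormal, median 9 J/min, log-SD 0.4 (24% above 12).
- Assumed outcome and test: 21% complications, two-sided 5% Wald test, N 1,500 or 4,000, hinge at 12 J/min for both exposures, no true interaction, no covariates, 800 replicates per cell (Monte Carlo error at most 1.8 points).

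**Step 3: planned model.** Entries are the percentage of significant product terms in the stated direction at N 1,500/4,000 (nominal 2.5%).

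| Log-odds slope per J/min, below → above 12 | Synergy, ρ = 0.1 | Synergy, ρ = 0.3 | Synergy, ρ = 0.5 | Antagonism, ρ = −0.3 |
|---|---|---|---|---|
| 0.08 → 0.084 (the plan's 5%) | 2/2 | 2/2 | 3/3 | 3/3 |
| 0.08 → 0.12 | 3/3 | 5/9 | 8/18 | 8/11 |
| 0.08 → 0.16 (doubled) | 3/4 | 9/19 | 24/49 | 19/42 |
| 0 → 0.08 | 5/9 | 16/39 | 37/71 | 18/32 |
| 0 → 0.15 | 8/15 | 38/76 | 74/99 | 46/83 |

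At ρ = 0 two-sided rejection is 5 to 8%. Repeat runs at ρ = 0.3 gave 9 to 11% / 18 to 19% for the doubled slope and 38 to 40% / 75 to 79% for flat then 0.15, hence the rounded 10/18% and 39/77%.

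**Step 4: milder settings at ρ = 0.3.**

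- Chemical power linear at 0.04, hinge in mechanical power only: 5/13% (doubled) and 19/38% (flat then 0.15).
- Only 12% of patients above the mechanical threshold (log-SD 0.25), doubled slope: 9/17%.
- Trial in the model, correlation wholly between trials: 5/10% (doubled) and 19/46% (flat then 0.15). Half between trials: 9/15% and 31/65%.
- Correlation wholly due to one adjusted continuous confounder: 8/13% and 30/67%.

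**Step 5: spline main effects.** With five-knot restricted cubic splines for both exposures plus the product term, rejection was 1.5 to 4% on each side in all 50 null cells without covariates.

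**Step 6: masking.** At ρ = −0.3 with a doubled slope and a true product coefficient of 0.01 per (J/min)², the planned term detects synergy in 24/54% and the spline model in 46/88%.

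**The case against.** The strongest reply is that both conditions are undocumented. No correlation is given. The limitations section says that FiO₂ may be confounded by pulmonary risk and by the response to surgery and ventilation. A reader might infer that oxygen and mechanical power are therefore substantially correlated, but the text does not say so: zero cannot be assumed, yet neither size nor sign is known. This stands, and it is why the figures are a conditional range.

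Second, a reader might infer that the plan has no safeguard at all. That goes too far. The Secondary aim 1 splines, the threshold regression and Figure 3 would show marked curvature, and the stratified patterns do not need linear effects; two of them match on the other exposure. These give indirect warning. None is a formal interaction test that allows for curvature, and the pattern in which both exposures rise can show rising risk without any interaction.

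Third, giving both exposures the same hinge is unfavourable to the plan, whose primary hypothesis is that chemical power contributes less. This also stands. With a weak, linear chemical effect, false synergy is roughly halved in the flat-then-steep case and falls less in the doubled-slope case.

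Fourth, a linear-by-linear product is a common first specification, and this is a secondary aim of an analysis that declares itself observational. That limits the weight of the point but does not remove it.

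**Conclusion.** The point holds as a conditional robustness gap. It needs two things together: a dose-response that bends markedly, and an appreciable correlation between the two exposures. At correlation 0.3 false synergy then ranges from about 5/13% (threshold in mechanical power only, doubled slope) to about 39/77% (both flat and then steep), against a nominal 2.5%. At correlation 0.1 it exceeds 5% only in the flat-then-steep shapes. With the 5% slope change that the plan calls clinically relevant, or with no correlation, the planned test is close to nominal. Covariate adjustment reduces the error without removing it.

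All of this rests on the assumed sample size, complication rate, slopes, threshold and correlations. The documents therefore do not support a conclusion that the planned test is invalid, or that a synergy found with it would be an artefact. They support only that, under the authors' own threshold hypothesis, the planned product term may not separate the two explanations. The point is one to consider, as a cheap improvement to a secondary analysis.

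**What to change.** Add to Secondary aim 2 in section 3.6.2:

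> The interaction term will also be tested in a model with the Secondary aim 1 cubic spline terms for both exposures as main effects (same confounders; knots fixed before the interaction is fitted). Both interaction estimates will be reported side by side with 95% confidence intervals, together with the correlation between the two time-weighted averages overall and by trial. Synergy seen only in the linear model will be interpreted with caution, in light of the Aim 1 curves.

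Do not attach an automatic rule that declares the interaction indistinguishable from curvature whenever the two models differ in sign or significance. With exactly linear effects and no interaction, such a rule fired in 20 to 24% of runs at correlation 0.3 and in 30 to 34% at 0.5, mostly because two near-zero estimates differed in sign. With a true interaction at correlation 0.5 it fired in 40 to 42% (N 1,500) and 26 to 29% (N 4,000). It would often blame curvature that is not there.

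The cost is one more model, using spline terms that are already planned, and lower power for the spline-based test if effects are truly linear and the exposures are correlated. With slope 0.08 and product coefficient 0.01, power at N 4,000 falls from 94% to 89% at correlation 0.3 and from about 96% to 69% at 0.5. At N 1,500 it falls from 56% to 47% and from 60% to 32%. With no correlation almost nothing is lost. Using three knots recovers little. The planned estimate is still reported.

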3. METHODS

3.1 Study Design and Population

We will perform a post hoc analysis of the previously combined dataset named 'Re-evaluation of the Effects of High PEEP with Recruitment Manoeuvres versus Low PEEP without Recruitment Manoeuvres During General Anaesthesia for Surgery' (REPEAT), registered at ClinicalTrials.gov: NCT03937375 on 3rd May 2019. This dataset merged the individual patient data from three RCTs, the 'High versus low positive end-expiratory pressure during general anesthesia for open abdominal surgery' (PROVHILO) study (registered with Controlled-Trials.com: ISRCTN70332574), the 'Individualized perioperative open-lung approach versus standard protective ventilation in abdominal surgery' (iPROVE) study (registered with ClinicalTrials.gov: NCT02158923) and the 'Effect of intraoperative high positive end-expiratory pressure with recruitment manoeuvres vs low PEEP on postoperative pulmonary complications in obese patients' (PROBESE) study (registered with ClinicalTrials.gov: NCT02148692).

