3.4.1 Primary Exposure

Chemical power calculated according to Lilien et al. [Lilien et al. 2023]:

Step 1: Estimation of local superoxide (O_2^-) production ($Pulm_{ROS}$) from lung oxygen consumption as a function of F_iO_2

$$Pulm_{ROS} = 1.7 * 10^{-5} + ((F_iO_2 - 0.21) * 1.63 * 10^{-4}) \text{ (mol/min)}$$

Step 2: Calculate chemical power (CP) from step 1 based on the first electron affinity of oxygen (141 kJ/mol).

$$CP = 141000 * Pulm_{ROS} \text{ (J/min)}$$

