3.6.4 Sample size considerations

We do not perform a formal power calculation; instead, the available number of patients in the pooled dataset serves as the sample size.

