3.6.5 Limitations

We are aware of several limitations of our analyzes. (1) Although the database was derived from trials, our study is observational, meaning we may detect associations but not establish causality. (2) Due to a widespread use of lung-protective mechanical ventilation exposure to higher ranges of mechanical power is presumably rare. (3) The use of supplemental oxygen (FiO₂) is potentially highly confounded by underlying pulmonary risk and patients' intraoperative responses to surgery and mechanical ventilation. (4) The underlying trials used slightly different definitions of postoperative pulmonary complications, adding further variability and potential bias to the results.

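### The pooled chemical-by-mechanical power term is unprotected if the three trials differ both in exposure level and in exposure slope

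*Combined protocol and SAP*

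**What the plan says.** Section 3.1 describes the source: "This dataset merged the individual patient data from three RCTs". Going by their titles, one trial enrolled open abdominal surgery, one abdominal surgery and one obese patients.

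Secondary Hypothesis 2 (2.2) is that "Chemical power-related harm largely depends on the concomitantly applied mechanical power". Section 3.6.2 tests it by "implementing an interaction term for the intraoperatively applied time-weighted average mechanical power in the multivariable regression model performed to evaluate the primary aim", which I read as a single CP x MP product.

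Trial appears only in the starred list of potential confounders in 3.6.1. For the primary-aim model, 3.6.2 states: "The regression model will be calculated with and without the above-mentioned confounders". One version therefore has no Trial term. In the other, a confounder may be dropped when it moves both exposure coefficients by less than 10%. That rule looks at the two exposure coefficients and not at the product term.

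The plan contains no trial-by-exposure terms, random slopes, within-trial centring or trial-specific interaction estimates. The stratified subsets and the 3D surface are also described on the pooled population. Section 3.6.5 notes that "The underlying trials used slightly different definitions of postoperative pulmonary complications" and that this may add bias, but plans nothing for the interaction.

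**The concern.** A Trial main effect lets each trial have its own baseline risk. It does not let each trial have its own MP slope or CP slope. By the formula in 3.4.1, CP is a linear function of FiO2 alone. If one trial ran at a higher mean FiO2, CP partly identifies that trial. If MP is also more (or less) strongly related to complications in that trial, the product term is the only term in the model that can represent the difference, and it will take up part of it. The mirror case works the same way: a trial with higher mean MP and a different CP slope.

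Unequal slopes are conceivable from the documents. Table 1 differs by trial for mild and severe respiratory failure, ARDS, pulmonary infection, atelectasis and bronchospasm. The populations differ, and MP (3.4.2) is an absolute quantity built from peak pressure, so one J/min need not mean the same load in obese and other patients.

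At stake is the reading of Secondary Hypothesis 2. Synergy could be reported, or a real synergy masked, because of how the trials differ and not because CP modifies MP-related harm within any of them.

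**Working it through.** The plan gives no figure to reproduce: no alpha for this test, no trial-level exposures, and for size only that "the available number of patients in the pooled dataset serves as the sample size". The check is therefore algebra plus simulation under stated assumptions.

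**CP scale (3.4.1).** CP = 141000 x (1.7e-5 + (FiO2 - 0.21) x 1.63e-4), so the slope is 141000 x 1.63e-4 = 22.98 J/min per unit FiO2. CP is 6.76 J/min at FiO2 0.4 and 15.96 at 0.8. A trial difference of 0.15 in mean FiO2 is 3.45 J/min; a difference of 0.35 is 8.04 J/min.

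**Mechanism.** Let the log-odds in trial k be a_k + b·CP + g_k·MP, with no interaction in any trial. The planned model forces the MP slope to be g + d·CP. Within trials d is 0. Between trials, d would be (difference in MP slope) / (difference in mean CP). The fitted d is roughly the between-trial value times w, the between-trial share of the FiO2 variance. For three equal trials with one shifted by D, w = (2/9)D² / [(2/9)D² + SD²]. With a slope difference of 0.05:

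| Mean FiO2 | SD | w | 0.05 / CP difference | Approximate d | Simulated mean d |
|---|---|---|---|---|---|
| 0.4/0.8/0.4 | 0.08 | 0.0356/0.0420 = 0.85 | 0.05/9.19 = 0.0054 | 0.0046 | 0.0044 |
| 0.4/0.5/0.4 | 0.08 | 0.0022/0.0086 = 0.26 | 0.05/2.30 = 0.0218 | 0.0056 | 0.0048 |
| 0.45/0.50/0.45 | 0.15 | 0.0006/0.0231 = 0.024 | 0.05/1.15 = 0.0435 | 0.0010 | 0.0010 |

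Only the part of the slope difference aligned with mean CP is absorbed, and little of it when FiO2 overlaps strongly.

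**Simulation 1.** Assumed: 1000 patients per trial, 30% risk, MP means 9/9/12 and SD 3 J/min, CP log-odds slope 0.03 per J/min unless stated, no true interaction, 600 runs, two-sided 5% Wald test. Simulation error near 5% is sqrt(0.05 x 0.95/600) = 0.9 points.

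| Mean FiO2 (SD) | MP slopes | Rejection, Trial main effect | Rejection, plus Trial x CP and Trial x MP |
|---|---|---|---|
| 0.4/0.8/0.4 (0.08) | 0.05 in all | 3.2% | 6.3% |
| 0.5 in all (0.12) | 0.05/0.10/0.05 | 5.2% | 4.3% |
| 0.4/0.8/0.4 (0.08) | 0.05/0.10/0.05 | 32% | 4.7% |
| 0.4/0.8/0.4 (0.08) | 0.05/0.15/0.05 | 88% | 5.5% |
| 0.4/0.5/0.4 (0.08) | 0.05/0.10/0.05 | 12% | 5.5% |
| 0.45/0.50/0.45 (0.15) | 0.05/0.10/0.05 | 8% | 6.5% |
| 0.4/0.8/0.4 (0.08) | 0.10/0.05/0.10 | 32%, sign reversed | 3.5% |
| 0.5 in all (0.12); CP slopes 0.03/0.03/0.08 | 0.05 in all | 13% | 4.7% |

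The first two rows have only one of the two differences. The last row is the mirror case: Trial x MP alone leaves it at 12.8%, so both sets of terms are needed. With 300 per trial, the third row gives 13%.

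**Simulation 2.** Assumed: trial sizes 900/1000/2000, MP means 8/9/11 and SD 3, MP slope 0.03 and mean FiO2 0.45 except in one of the two smaller trials, no true interaction, Trial kept.

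| That trial's FiO2 | Its MP slope | Rejection, SD 0.08 | Rejection, SD 0.15 |
|---|---|---|---|
| 0.60 | 0.06 | 11-13% | about 8% |
| 0.60 | 0.09 | 26-28% | about 12% |
| 0.80 | 0.06 | 12-15% | about 12% |
| 0.80 | 0.09 | 44-51% | about 34% |

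If the largest trial is the one that differs, the SD 0.08 figures reach 38% at 0.60 and 60-65% at 0.80. With Trial x CP and Trial x MP added, rejection is about 2-8% throughout.

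**Precision.** The added terms raise the standard error of CP x MP by about 9% with equal FiO2, by 18-37% at a 0.15 difference and by 52-123% at 0.35 (within-trial SD 0.15 to 0.08).

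**The case against.** The strongest reply is that the bias needs two facts together, and the documents give neither. Mean FiO2 must differ by trial and the MP slope must differ in line with it (or the mirror pair). That is correct, and it limits the point to a risk.

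The suggested causes of unequal slopes are also uncertain. If the outcome definitions act mainly as different severity cut-offs, they shift baseline frequency, which the Trial term handles. A doubling or tripling of the slope is an assumption, and the result is sensitive to the within-trial FiO2 SD. Both points stand.

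The within-trial estimate has its own price. If the slopes are in fact equal, the pooled test is valid and the extra terms discard good information. With a true interaction of 0.006 per (J/min)², equal slopes and SD 0.08, power fell from 54-57% to 17-19% at FiO2 0.80, and from 26% to 16% at 0.60. The sample is fixed, so this cannot be recovered. Within-trial contrasts also remain exposed to the patient-level confounding of FiO2 that 3.6.5 concedes. This defeats the idea of replacing the pooled test outright. It does not defeat reporting the two side by side.

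Finally, this is a secondary aim of a post hoc analysis that disclaims causality, and the plan states no alpha or decision rule for it. That lowers the stakes. But the displays that accompany the test are pooled too, so nothing planned would reveal the problem.

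**Conclusion.** The concern holds as an unguarded risk in the test of Secondary Hypothesis 2. With Trial as a main effect only, the pooled CP x MP coefficient mixes within-trial and between-trial information, and the false signal can take either sign. Under the Simulation 2 assumptions with a smaller trial as the outlier, false rejection at a nominal 5% is about 8% to 50%. It is higher if the largest trial is the outlier or the contrasts are more extreme, and about 5% if only one condition holds. All of these figures rest on assumed trial sizes, FiO2 distributions, MP means and slopes.

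Three stronger readings are tempting and are not supported:

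- A reader might infer that the planned interaction will be false. The documents do not show that the trials differ in FiO2, MP or slope.
- A reader might infer that any slope difference passes into the product term. Only the part aligned with the trial means does.
- A reader might infer that the pooled test should be abandoned. That would lose valid information if the slopes are equal.

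This is a cheap improvement to the SAP, not a fatal flaw.

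**What to change.** In 3.6.2, secondary aim 2:

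1. Keep Trial in the interaction model whatever the 10% rule indicates.
2. Pre-specify a second fit that adds Trial x CP and Trial x MP (two terms each, 4 df), so that its CP x MP coefficient rests on within-trial contrasts.
3. Report the pooled and within-trial CP x MP coefficients side by side, each with its 95% CI.
4. Claim synergy only if the two agree in direction and size, and state in advance what counts as agreement, because a wide within-trial interval is compatible with many values. If they diverge, attribute the pooled result to possible between-trial differences.
5. Tabulate FiO2, CP and MP by trial, so that readers can see whether the exposure levels differ.

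The cost is SAP wording, four model terms and one table, with no new data. The within-trial estimate is less precise by the amounts shown above, most so where trial FiO2 levels are far apart. For that reason it stands beside the pooled term and does not replace it.

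### The four-pattern analysis behind Figure 4, as specified, does not compare the chemical power effect at low and high mechanical power, and a steep both-rising panel is not evidence of synergy

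*Combined protocol and SAP*

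**What the plan says.** Secondary Hypothesis 2 (section 2.2) is a statement of effect modification: "Chemical power-related harm largely depends on the concomitantly applied mechanical power", spelled out as "chemical power causes significantly more postoperative pulmonary complications within seven days after surgery when exposed to high intraoperative mechanical power". The last paragraph of the Background likewise expects a synergistic interaction.

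Section 3.6.2, Secondary aim 2, names the formal analysis first: "We will evaluate the interaction between chemical power and mechanical power by implementing an interaction term" in the model used for the primary aim. A stratified analysis is added to it, run "for 5 subsets of the study population stratified by chemical or mechanical power for each of the following patterns". The first two patterns each vary one exposure while the other is held: "1) increasing chemical power and matched mechanical power, 2) matched chemical power and increasing mechanical power". In the remaining two, both exposures change from subset to subset: "3) increasing chemical power and decreasing mechanical power, and 4) increasing chemical power and increasing mechanical power". The level at which the other exposure is matched in patterns 1 and 2 is not stated, and no second matched level is requested.

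Section 3.6.3 turns the four patterns into panels a to d of Figure 4, which is to show "corresponding relative risks of PPC, calculated for each subsample; error bars represent the 95% confidence interval". It names no reference group for those relative risks, no shared cut-points, no contrast between panels and no values expected without interaction. Figure 5 is a separate 3D surface of PPC percentage over both exposures.

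**The concern.** To see whether chemical power (CP) is more harmful at high mechanical power (MP), the CP gradient at low MP has to be set beside the CP gradient at high MP. Pattern 1 gives one CP gradient at one unstated MP level, and pattern 2 gives one MP gradient. Patterns 3 and 4 change both exposures at once.

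Pattern 4 looks most like the stated hypothesis, because it ends where both exposures are high. Its rise, however, contains the main effect of CP and the main effect of MP as well as any interaction. A reader who compares panel d with panel a or b may take the sum of two main effects for synergy. The sample size is whatever the pooled dataset provides, without a power calculation (section 3.6.4). The product term may therefore be imprecise, and readers may then lean on the picture.

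**Working it through.** The documents give no PPC rate, effect size or patient number, so there is no figure of the plan's own to reproduce. All numerical inputs below are assumptions.

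**Check 1: steepness without interaction.** Five subsets, k = 0 to 4. The lowest subset has risk p0, each exposure has the same odds ratio (OR) per step, and the product term is exactly 1. Patterns 1 and 4 start from the same lowest cell. Pattern 1 odds are p0/(1−p0) × OR^k; pattern 4 odds are p0/(1−p0) × OR^(2k).

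For p0 = 20% (odds 0.25) and OR 1.3:
- Pattern 1 at k = 4: 0.25 × 1.3^4 = 0.25 × 2.856 = 0.714, so risk 41.7% and relative risk (RR) 2.08.
- Pattern 4 at k = 4: 0.25 × 1.3^8 = 0.25 × 8.157 = 2.039, so risk 67.1% and RR 3.35.

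| Lowest-subset risk | OR per step | RR, pattern 1 | RR, pattern 4 |
|---|---|---|---|
| 20% | 1.2 | 1.71 | 2.59 |
| 20% | 1.3 | 2.08 | 3.35 |
| 10% | 1.3 | 2.41 | 4.75 |

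**Check 2: matching at the centre instead.** Scale both exposures from −1 to 1 and let logit(p) = b0 + b1·CP + b2·MP + b3·CP·MP. With 20% risk at the centre, OR 1.5 per half-range for each exposure and b3 = 0, panels a and b run from 14.3% to 27.3% (RR 1.91), panel c is flat at 20% (RR 1.00), and panel d runs from 10.0% to 36.0% (RR 3.60). Over centre risks of 10% to 40% and ORs of 1.2 to 1.5, panel d ranges from RR 1.55 to 4.25, and panels a and b from 1.24 to 2.07.

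**Check 3: does panel d respond to interaction?** End to end, panel d gives (b0+b1+b2+b3) − (b0−b1−b2+b3) = 2b1 + 2b2, so b3 cancels. With the ORs of 1.5 above, its OR is 1.5^4 = 5.06 whatever the interaction. Its RR is 3.60 with none, 3.35 with synergy (interaction OR 1.3) and 3.83 with antagonism (0.77). Panel c gives 2b1 − 2b2, and b3 cancels again. If each panel uses its own lowest subset as reference, no combination of these two end-to-end log odds ratios yields b3.

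**Check 4: what does carry the interaction?** The end subsets of panel d are low/low and high/high; those of panel c are low/high and high/low. The CP odds ratio at high MP divided by that at low MP is exp(4·b3), again with main ORs of 1.5:
- no interaction: 2.25 / 2.25 = 1.00
- interaction OR 1.3: 3.80 / 1.33 = 2.86
- interaction OR 0.77: 1.33 / 3.79 = 0.35

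The contrast can be formed if absolute risks, or relative risks against one common reference, are shown. It is imprecise. With independent exposures cut at quintiles, a corner cell holds 1/25 of the patients, or 80 of an assumed 2,000. The variance of the log ratio is 1/(80×0.10×0.90) + 2/(80×0.20×0.80) + 1/(80×0.36×0.64) = 0.349, so the standard error is 0.59; with 4,000 patients it is 0.42.

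**Check 5: scale.** Under the no-interaction model of check 1 (20%, OR 1.3), CP at the lowest MP takes risk from 20% to 41.7%, RR 2.08. At the highest MP it takes risk from 41.7% to 67.1%, RR 1.61. Compared as relative risks this looks like antagonism; compared as risk differences (21.7 against 25.4 points) it looks like synergy. Only the odds ratio, 2.86 in both, agrees with a product term of 1.

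**The case against.** The strongest reply is that the aim does not depend on Figure 4. The product term tests whether the CP effect changes with MP, the stratified patterns are an addition, and Figure 5 shows both exposures jointly. This stands. A reader might infer that Secondary aim 2 has no valid test; section 3.6.2 plainly provides one.

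A reader might also infer that Figure 4 is incapable of showing an interaction. That goes too far: check 4 shows that the end subsets of patterns 3 and 4 together contain the four cells required. What is missing is the specification, namely a common reference, shared cut-points and a stated contrast.

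Nor is panel d bound to mislead. The effect needs both exposures to be harmful. If CP has no effect, panel d equals panel b (RR 1.91 for both, with MP OR 1.5 per half-range and 20% centre risk). With a weak CP effect (OR 1.1) panel d is 2.22 against 1.91 in panel b. The primary hypothesis expects CP to contribute less than MP, so the excess over panel b may be modest. The plan also nowhere says that panel d's slope will be read as a test.

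What remains is that the product term does not correct a figure that can appear to contradict it, and that harm from both exposures is the case the protocol contemplates, since section 2.2 seeks harm thresholds for each.

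**Conclusion.** The point holds for the supplementary stratified analysis and its figure, not for the formal test of Secondary aim 2. As specified, the four patterns do not compare the CP effect at low and high MP. When both exposures are harmful and there is no interaction on the log-odds scale, the both-rising panel is steeper than either matched panel: RR 3.35 against 2.08 with 20% risk in the lowest subset and OR 1.3 per step, assuming equal steps from a common starting cell. The direction is the same across the other inputs tried; the size depends on them, and none comes from the documents. With the matched panels at the centre, panel d's end-to-end slope hardly changes with true interaction, so its steepness is not evidence of synergy. No formal test or primary result is affected. The change is worth making because it is cheap and this figure supports the interaction aim.

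**What to change.** In section 3.6.2 and Figure 4:

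- Estimate the CP odds ratio within the lowest and within the highest MP tertile, with the same CP cut-points or per-unit scale in both. Do the mirror image for MP within the lowest and highest CP tertiles.
- Report the ratio of the two odds ratios with its 95% CI. Keep to the odds-ratio scale, which is that of the product term; a difference in relative risks would bring back the distortion in check 5.
- Use one common reference group across all panels.
- Label patterns 3 and 4 as descriptive, and state that interaction is judged by the model term.

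The cost is SAP wording and a redrawn figure, with no new data. The drawback is smaller strata and wider intervals. As a rough guide, with independent exposures a corner of a tertile grid holds 1/9 of the patients. At the cell risks of check 4 and an assumed 2,000 patients, the standard error of the log ratio is 0.59 × √(9/25) = 0.35, so the 95% CI runs from about half to twice the estimate (exp(1.96 × 0.35) ≈ 2.0). Correlated exposures would thin some corners further. If cells are thin, use three exposure steps instead of five, or the per-unit odds ratio.
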